The BOR is defined as a single best response status at any tumor response assessment after first administration of IMP and prior to or at the start date of the first subsequent anti-cancer therapy. Overall response of PD within 14 days after the start date of the first subsequent anti-cancer therapy will be considered.

Only responses up to and including the date of the first progressive disease will be considered in the derivation of the BOR.

The following order of tumor response categories will be used, with “Complete Response” is the best category:

Complete Response (CR) – Partial Response (PR) – Stable Disease (SD) – Progressive Disease (PD) – Not Evaluable (NE) – Not Applicable (NA).

Best Overall Response (BOR) based on iRECIST (central reading):

The following order of tumor response categories will be used to define the BOR category based on iRECIST (central reading), with “Complete Response” is the best category:

Complete Response (iCR) – Partial Response (iPR) – Stable Disease (iSD) - Unconfirmed Progressive Disease (iUPD) – Confirmed Progressive Disease (iCPD) – Not Evaluable (NE) – Not Applicable (NA).

Only central reading assessments after first administration of IMP and prior to or at the start date of the first subsequent anti-cancer therapy will be considered in the derivation. Overall response of iUPD or iCPD within 14 days after the start date of the first subsequent anti-cancer therapy will be considered.

Only responses up to and including the date of the first progressive disease will be considered in the derivation of the BOR.

Further information on the definition of the BOR based on iRECIST is available in Section [13.3](#).

PSA Response definition based on PCWG3:

PSA response definition based on PCWG3 will be derived based on the PSA response data reported by the investigator.

If a PSA PD occurred \geq 12 weeks after first administration of IMP. This PSA PD needs no confirmation.

For the derivation of best overall PSA Response based on PCWG3, the PSA responses have to be **confirmed**. The following rules have to be implemented for PSA response confirmation:

- **PSA PR Response Confirmation**
 - PSA PR needs to be confirmed by:
 - Subsequent [Radiological Soft Tissue PR or CR response] or
 - Subsequent [PSA PR response]

- Which occurs within ≥ 20 days and \leq start date of first subsequent anti-cancer therapy, immediately after initial PSA PR response

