8.7.4.1 Exploratory efficacy endpoints

Objective Response Rate based on iRECIST (central reading)

ORR based on iRECIST will be analyzed for mCRPC patients in Part 1 and Part 2 only.

The ORR is defined as the number of patients with iCR or iPR as best objective response per iRECIST divided by the number of patients in the mITT set. Patients not meeting the criteria for iCR or iPR, including those without any post-baseline tumor assessments, will be considered as non-responders. The ORR will be summarized with absolute and relative frequencies along with two-sided 95% Clopper-Pearson CIs by treatment group.

BOR (all categories) will be summarized with absolute and relative frequencies.

Tumor response assessment including overall response and BOR will be listed. In addition, listings including all tumor assessments per iRECIST (central reading) (target lesion, non-target lesion, new lesion) will be generated.

Duration of Response

DoR will be analyzed for Part 1 and Part 2 Arms 1A and 1B only. DoR will be analyzed separately for PCWG3 and iRECIST (central reading).

The DoR is defined as the time from the date of first radiographic documented OR to the date of first disease progression or death from any cause, whichever occurs first. Only patients who experience a confirmed OR will be analyzed for DoR.

In case death date is reported after trial discontinuation date, these death details will not be considered in the DoR analysis. The patient will be censored at the day of the last response assessment.

DoR will be analyzed using the Kaplan-Meier method. Kaplan-Meier plots will be generated.

Patients alive and without disease progression at data cut-off date or patients lost to follow-up will be censored at the day of their last response assessment.

Only response assessments prior to or at the start date of the first subsequent anti-cancer therapy will be considered for DoR analysis. PD within 14 days after the start date of the first subsequent anti-cancer therapy will be considered.

DoR based on PCWG3:

OR is defined as CR or PR. Disease progression is defined as tumor response = Progressive Disease (PD)

DoR expressed in months for patients whose objective response was confirmed CR or PR
= (MIN [Date of first documented disease progression (PD), date of death from any cause]
– Date of first documented overall response (CR or PR) + 1) / 30.4375 for events

or

(Date of the last evaluable response assessment – Date of first documented overall

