Patients not meeting the criteria for CR or PR (iCR or iPR per iRECIST (central reading)), including those without any post-baseline response assessments, will be considered as non-responders. The ORR will be summarized with absolute and relative frequencies along with two-sided 95% Clopper-Pearson CIs.

BOR (all categories) will be summarized with absolute and relative frequencies.

Duration of Response based on PCWG3 or iRECIST (central reading)

DoR will be analyzed separately for PCWG3 and iRECIST (central reading).

The DoR is defined as the time from the date of first radiographic documented OR to the date of first disease progression or death from any cause, whichever occurs first. Only patients who experience a confirmed OR after start of cemiplimab treatment will be analyzed for DoR.

Only death dates reported prior to or at the date of trial discontinuation will be considered in the DoR analysis.

DoR will be analyzed using the Kaplan-Meier method. Kaplan-Meier plots will be generated.

Patients alive and without disease progression at data cut-off date or patients lost to follow-up will be censored at the day of their last response assessment.

Only response assessments prior to or at the start date of the first subsequent anti-cancer therapy will be considered for DoR analysis. PD within 14 days after the start date of the first subsequent anti-cancer therapy will be considered.

DoR based on PCWG3:

OR is defined as CR or PR. Disease progression is defined as tumor response = Progressive Disease (PD)

DoR expressed in months for patients whose objective response was confirmed CR or PR after start of cemiplimab treatment =

(MIN [Date of first documented disease progression (PD) after start of cemiplimab treatment, date of death from any cause] – Date of first documented overall response (CR or PR) + 1) / 30.4375 for events

or

(Date of the last evaluable response assessment after start of cemiplimab treatment – Date of first documented overall response (CR or PR) + 1) / 30.4375 in case of censoring.

DoR based on iRECIST (central reading):

OR is defined as iCR or iPR. Disease progression is defined as tumor response = Confirmed progressive disease (iCPD)

DoR expressed in months for patients whose objective response was confirmed iCR or iPR after start of cemiplimab treatment =

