13.3 Appendix 3: Best Overall Response derivation for iRECIST

Scenarios of assignments of best overall response (iBOR) using iRECIST, based on Seymour at all (2017) [4]

	Time point response 1	Time point response 2	Time point response 3	Time point response 4	Time point response 5	iBOR
Example 1	iCR	iCR, iPR, iUPD, or NE	iCR, iPR, iUPD, or NE	iUPD	iCPD	iCR
Example 2	iUPD	iPR, iSD, or NE	iCR	iCR, iUPD, or NE	iCR, iPR, iSD, iUPD, iCPD, or NE	iCR
Example 3	iUPD	iPR	iPR, iSD, iUPD, or NE	iPR, iSD, iUPD, NE, or iCPD	iPR, iSD, iUPD, NE, or iCPD	iPR
Example 4	iUPD	iSD or NE	iPR	iPR, iSD, iUPD, or NE	iPR, iSD, iUPD, iCPD, or NE	iPR
Example 5	iUPD	iSD	iSD, iUPD, or NE	iSD, iUPD, iCPD, or NE	iSD, iUPD, iCPD, or NE	iSD
Example 6	iUPD	iCPD	Any	Any	Any	iCPD
Example 7	iUPD	iUPD (no iCPD)	iCPD	Any	Any	iCPD
Example 8	iUPD	NE	NE	NE	NE	iUPD

Eight examples are presented for patients with target disease at baseline, but many more scenarios exist following the same principles. Table assumes a randomised study in which confirmation of complete response or partial response is not required. For patients with non-target disease only at baseline, only iCR or non-complete response or non-progression of disease can be assigned at each time point (not shown in the table for ease of presentation). “i” indicates immune responses assigned using iRECIST. iBOR=best overall response. iCR=complete response. iPR=partial response. NE=not evaluable. iUPD=unconfirmed progression. iCPD=confirmed progression. iSD=stable disease. RECIST=Response Evaluation Criteria in Solid Tumours.

See iRECIST guidelines and wording about Best Objective response. See tables 1 and 2 as well from this paper:

“Although the principles of the assignment of the time point response and best overall response closely follow RECIST 1.1, and reflect assessment of target and non-target lesions as well as the presence of new lesions, the possibility of pseudoprogression adds complexity (tables 1–3, panel 2, appendix pp 2–4). The time point response is calculated using the response assigned for each category of lesion (as for RECIST 1.1), but takes into account the last time point response.

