The algorithm for patients with no previous iUPD is identical to RECIST 1.1. For patients with iUPD at the last time point response, the next time point response is dependent on the status of all lesions, including target, non-target, new lesion target, and new lesion non-target; on whether any increase in size has occurred (either a further increase in size or a sufficient increase to assign a new iUPD if the criteria were not previously met); or the appearance of additional new lesions.

For iRECIST, the best overall response (iBOR) is the best time point response recorded from the start of the study treatment until the end of treatment, taking into account any requirement for confirmation. iUPD will not override a subsequent best overall response of iSD, iPR, or iCR (tables 1–3, appendix pp 2–4), meaning that iPR or iSD can be assigned (time point response or iBOR) even if new lesions have not regressed, or if unequivocal progression (non-target lesions) remains unchanged, providing that the criteria for iCPD are not met.”

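### SAP 8.2 does not say whether iRECIST best response stops at unconfirmed or confirmed progression; read literally it stops at the first iUPD, which contradicts SAP Appendix 3

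*SAP*

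**What the plan says.** SAP 8.2 (Key definitions) derives iRECIST best overall response from central-reading assessments, using a fixed order of categories. The lower end of that order reads "Unconfirmed Progressive Disease (iUPD) – Confirmed Progressive Disease (iCPD) – Not Evaluable (NE"), so iUPD ranks above iCPD and both carry a progressive-disease label.

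Two rules on timing follow. The first deals with subsequent anti-cancer therapy: "Overall response of iUPD or iCPD within 14 days after the start date of the first subsequent anti-cancer therapy will be considered". The second is the cut-off: "Only responses up to and including the date of the first progressive disease will be considered in the derivation of the BOR". The same cut-off sentence stands in the soft-tissue and PCWG3 definitions of best response, where progression is a single category. The iRECIST paragraph then ends with a pointer: "Further information on the definition of the BOR based on iRECIST is available in Section" 13.3.

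Section 13.3 (Appendix 3) reproduces the iRECIST assignment table and guideline text, including "iUPD will not override a subsequent best overall response of iSD, iPR, or iCR". It introduces its table with "Eight examples are presented for patients with target disease at baseline" and adds that further scenarios exist.

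For iRECIST duration of response, SAP 8.7.4.1 does name the event: "Disease progression is defined as tumor response = Confirmed progressive disease (iCPD"). For iRECIST ORR the same section says "The ORR is defined as the number of patients with iCR or iPR as best objective response per iRECIST", over the mITT set, so ORR takes over whatever the best-response derivation produces.

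**The concern.** Where progression has only one category, the cut-off sentence is clear. Under iRECIST there are two. The sentence just before the cut-off puts iUPD and iCPD together where the other definitions have PD. A programmer working from 8.2 alone would reasonably stop at the first iUPD. One working from 13.3 would carry on to iCPD. The same scans would then give two different best responses.

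The patients affected are those with apparent progression followed by response, which is the situation Appendix 3 sets out to handle. At stake are the exploratory iRECIST ORR in the mCRPC groups, entry to iRECIST duration of response, and the matching analyses of Arm 1B patients who switch to cemiplimab (SAP 8.7.4.2). The two endpoints would also fit together badly: duration of response runs through iUPD to iCPD, yet a literal cut-off could discard the response that starts its clock.

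**Working it through.** The plan states no figure on this point, so the benchmark is the iBOR column printed in Appendix 3.

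**Inputs.** The response sequences and printed iBOR for the eight examples come from SAP 13.3. The order iCR > iPR > iSD > iUPD > iCPD > NE comes from SAP 8.2.

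**Rule applied.** Best response is the highest-ranked category among the assessments up to and including the stopping assessment. Every sequence that each example allows was run under two meanings of the cut-off. Within each example, all allowed sequences gave the same answer.

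| Example | Deciding sequence | Printed iBOR | Stop at first iUPD or iCPD | Stop at first iCPD only |
|---|---|---|---|---|
| 1 | iCR at the first assessment | iCR | iCR | iCR |
| 2 | iUPD; iPR, iSD or NE; iCR | iCR | **iUPD** | iCR |
| 3 | iUPD; iPR | iPR | **iUPD** | iPR |
| 4 | iUPD; iSD or NE; iPR | iPR | **iUPD** | iPR |
| 5 | iUPD; iSD | iSD | **iUPD** | iSD |
| 6 | iUPD; iCPD | iCPD | **iUPD** | **iUPD** |
| 7 | iUPD; iUPD; iCPD | iCPD | **iUPD** | **iUPD** |
| 8 | iUPD; NE from then on | iUPD | iUPD | iUPD |

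Bold marks disagreement with Appendix 3.

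**Splitting the disagreement.** The literal cut-off matches 2 of 8 examples and the iCPD cut-off matches 6 of 8. The cut-off wording therefore accounts for 6 − 2 = 4 examples (2 to 5). In three of these (2, 3 and 4) the patient moves from responder to non-responder. Example 5 loses iSD, which does not enter ORR.

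The other two (6 and 7) fail under both cut-offs. Their cause is the category order: with iUPD ranked above iCPD, a patient whose progression is confirmed keeps iUPD as the best category. Neither category is a response, so this does not change ORR. It does change the table of best-response categories.

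**Size per patient.** With r responders among n patients, losing one changes ORR by r/n − (r − 1)/n = 1/n. At the planned stage sizes per mCRPC arm (SAP 6):

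- n = 20: 1/20 = 0.050, or 5.0 percentage points
- n = 33: 1/33 = 0.030, or 3.0 percentage points

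**Both corrections together.** With the cut-off at first iCPD, and iCPD assigned when iUPD is later confirmed with no iSD, iPR or iCR in between, Examples 6 and 7 become iCPD. Examples 1 to 5 and 8 stay as in the last column. All eight then match.

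**The case against.** The best answer is that the intended meaning can be recovered. SAP 8.2 lists the two kinds of progression separately, points to 13.3 directly after the cut-off, and 13.3 is explicit. Where the SAP does define iRECIST progression, for duration of response, it chooses iCPD. Reading the cut-off as iCPD reconciles all three places. This stands as evidence of intent, and it is why a reader should not conclude that responses after iUPD will certainly be discarded: a programmer who follows 13.3 would keep them. It does not settle the matter, because the pointer offers further information without saying that it overrides the stated limit, and the iCPD definition is given for duration of response only.

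A second objection is that few patients may be affected. Scheduled imaging ends at investigator-assessed progression (protocol 8.1.1.1), and the eight examples are illustrations, not a sample. That is fair. Later scans can still occur: the investigator may postpone a diagnosis of progression, protocol Appendix 9 provides for confirmatory scans, and the iRECIST reading is central and retrospective (protocol 8.1.1.2). The documents do not show how common this is.

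Three stronger inferences are tempting and are not supported:

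- **All six disagreements come from the cut-off.** Examples 6 and 7 come from the ranking.
- **The trial's main efficacy result is exposed.** The primary ORR and the futility rule use PCWG3 (SAP 8.7.1.1 and 8.7.6).
- **iRECIST PFS must also use iCPD as its event.** SAP 8.7.4.1 leaves that event unnamed, but choosing it is a separate decision with its own trade-off. A patient like Example 8 would never reach iCPD, and iCPD falls later than the first iUPD.

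**Conclusion.** The point holds as an unresolved conflict within the SAP. The cut-off in 8.2 does not specify iUPD or iCPD, and its literal reading contradicts Appendix 3 in four of the eight worked examples, three of them with a change in responder status. A second, independent conflict in the iUPD/iCPD ranking affects Examples 6 and 7 and leaves ORR untouched.

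The effect on iRECIST ORR is 1/n per affected patient. The values of 5.0 and 3.0 points assume mITT arms of 20 and 33. Enrollment of mCRPC patients stopped after the interim analysis and the final arm sizes are not given, so the actual step may differ. The total effect cannot be calculated without the number of patients who respond after iUPD.

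Only exploratory iRECIST endpoints are involved. The correction is still worth making, because a prespecified derivation should give one answer whichever section the programmer follows.

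**What to change.** Make two edits to the iRECIST paragraph of SAP 8.2:

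1. Change the cut-off to the first confirmed progressive disease (iCPD).
2. Align the iUPD/iCPD ranking with Examples 6 and 7 by assigning iCPD when an iUPD is later confirmed with no intervening iSD, iPR or iCR.

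The first edit alone repairs every example that bears on ORR but leaves Examples 6 and 7 in conflict, so both are needed. The cost is a few lines of SAP text and the matching change in the derivation program, with no new data. The table list in SAP 11.1.1 does not flag the iRECIST ORR table for the interim analysis, so under the plan the rule can be settled before that table is first produced.

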#### 2. MEASURES OF RESPONSE:

The PCWG3 criteria for disease response in a patient are considered met if 1 or more of the following conditions occur:

- a) PSA response:
- PR: \ge 50\% decline in PSA from baseline confirmed at least 4 weeks later
- SD: Serial PSA measurements that do not meet the criteria for PR or PD
- b) Radiological response:
- Soft tissue/visceral disease:
  - CR: Disappearance of all target lesions. A reduction in short axis to <10 mm must be seen in any pathological lymph nodes. No new lesions.
  - PR: 30% decrease in the sum of the longest diameter of target lesions.
  - SD: No evidence of PD, CR or PR.
- Bone disease response
  - Bone scan is not used as part of the response criteria. Bone scans will be evaluated for progression only.
- c) Circulating tumor cell (CTC) response:
- Conversion of CTC  $\geq 5/7.5$  mL to  $\leq 5/7.5$  mL at 9 weeks. If there is a CTC response, this must be confirmed by an additional  $\leq 5/7.5$  mL result at least 4 weeks later.

CONFIDENTIAL Page 114 of 122

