The rules for the definition of BOR based on PCWG3 are referring to the following data reported in the CRF:

- Confirmed PSA response reported by the investigator (see Section 8.2 for more details regarding PSA response confirmation)
- Radiological Soft Tissue Evaluation (response data collected in the CRF on the “RECIST 1.1” page)
- Clinical Progression (data collected in the CRF on the “Clinical Progression” page)
- Bone Disease Progression (data collected in the CRF on the “Bone Lesion” pages with Clinical Impression = Progression)

Only assessments after first administration of IMP and prior to or at the start date of the first subsequent anti-cancer therapy will be considered in the derivation. Overall response of PD within 14 days after start date of the first subsequent anti-cancer therapy will be considered.

Only responses up to and including the date of the first progressive disease will be considered in the derivation of the BOR.

Overall Response of CR, PR, SD per PCWG3 is based on radiological soft tissue response or confirmed PSA response.

Progression of Disease per PCWG3 is based on the earliest radiological soft tissue progression, Bone disease progression, confirmed PSA progression or clinical progression.

The following order of tumor response categories will be used, with “Complete Response” is the best category:

Complete Response (CR) – Partial Response (PR) – Stable Disease (SD) – Progressive Disease (PD) – Not Evaluable (NE) – Not Applicable (NA).

Derivation of PSADT:

PSADT will be derived based on the PSA measurements provided by the investigator in the database and collected during the trial at screening visit and during each cycle.

PSADT will be calculated post-treatment on C4D1 and D1 of every fourth subsequent cycle (e.g. C8D1, C12D1, etc.) in Part 1 and Part 2 Arms 1A and 1B, or on C4D1, C8D1, and EoT in Part 2 Arms 2 and 3.

PSA measurements reported after EoT visit or after start of the first subsequent anti-cancer therapy will not be considered in the derivation of PSADT.

PSADT will be calculated using a linear regression model of the natural logarithm of PSA values and time ([3] and [<https://drhaddad.com.au/wp-content/uploads/2022/07/13.pdf>], [8]).

Derivation of PSADT post-treatment at every fourth subsequent cycle:

1. Compute the slope of the regression line of natural logarithm of PSA vs. time (which is the number of doublings per unit time) where PSA is the PSA level in ng/mL at each time point

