8.7.3 Secondary analyses

8.7.3.1 Secondary efficacy endpoints

Prostate-specific antigen decline

PSA will be collected for all patients in Part 1 and Part 2 at several visits during the course of the trial (see SoA in Section 13.6 for more details). PSA values will be provided by a central laboratory and reported by the investigator in the database. For the analyses, it

was agreed to use the PSA measurements as provided by the investigator together with the PSA response per PCWG3 criteria as reported in the database.

PSA decline calculated as percentage change compared to baseline will be summarized using descriptive summary statistics for each visit by treatment group.

PSA decline of 0 to 25%, > 25% to 50%, and > 50% compared with baseline and PSA decline of <50% versus ≥50% compared to baseline will be summarized with absolute and relative frequencies (n and %) of patients by visit and treatment group for the mITT set.

Bar charts for PSA decline compared to baseline in the above defined categories by visit will be generated for the mITT set.

Waterfall plots for maximum PSA decline from baseline per patient will be generated.

For the derivation of maximum decline from baseline only measurements which were reported ≥ 4 weeks after treatment start and prior to or at the EoT visit and prior to or at the start date of the subsequent anti-cancer therapy to be considered. Only PSA measurements corresponding to a confirmed PSA response (see Section 8.2 for the definition of confirmed PSA response) or reported after a confirmed PSA response have to be considered in the derivation of maximum PSA decline (an initial PSA response will confirm all subsequent PSA responses of the same response value, as long as there is not a better or worse response between them).

PSA response per PCWG3 criteria (as reported by the investigator) will be summarized with absolute and relative frequencies (n and %) of patients by visit and treatment group for the mITT set.

Best overall PSA response, ORR and Clinical Benefit Rate (CBR) per PCWG3 criteria will be summarized for the mITT set.

Sensitivity analyses for PSA decline will be performed using the ITT set and the PP set depending on the number of patients excluded.

Prostate-specific antigen doubling time

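### PSA response can by itself make a patient a responder in the primary ORR, but it is taken from the investigator's reported category and no planned analysis derives it from the PSA values already collected

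*SAP*

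**What the plan says.** The chain from reported category to primary endpoint runs through SAP 8.2 and 8.7.1.1.

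- **Source of the category.** SAP 8.2: "PSA response definition based on PCWG3 will be derived based on the PSA response data reported by the investigator". The best overall response derivation in the same section lists as its PSA input "Confirmed PSA response reported by the investigator".
- **PSA alone suffices.** SAP 8.2: "Overall Response of CR, PR, SD per PCWG3 is based on radiological soft tissue response or confirmed PSA response". Protocol Appendix 9 agrees: "The PCWG3 criteria for disease response in a patient are considered met if 1 or more of the following conditions occur", and PSA response is one of the listed conditions.
- **Confirmation.** SAP 8.2 programs this step. A PSA partial response (PR) is confirmed by a later PSA PR, or by a soft-tissue PR or complete response (CR), at least 20 days on and with nothing worse in between. Appendix 9 asks for a fall of at least 50%, as a "decline in PSA from baseline confirmed at least 4 weeks later".
- **Origin of the values.** SAP 8.7.3.1: "PSA values will be provided by a central laboratory and reported by the investigator in the database". Protocol Table 10-2 lists PSA among the central tests. SAP 8.7.3.1 adds that it "was agreed to use the PSA measurements as provided by the investigator together with the PSA response per PCWG3 criteria" as entered in the database, and gives no reason.
- **Use.** SAP 8.7.1.1 counts CR or PR per PCWG3 as the primary ORR and tests it against 5% in each arm. SAP 3.2 describes the trial as open-label.

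**The concern.** A fall of at least 50% from a defined baseline, seen again after a set interval, needs no judgement once the values and dates are recorded. The SAP nevertheless takes the per-visit PR, stable disease (SD) or progressive disease (PD) category as the investigator entered it, and only then applies its programmed confirmation. Errors of classification or transcription, made by staff who know the treatment, can therefore pass into the primary endpoint unchecked.

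Errors can run both ways. A wrong PR can add a responder. A wrong PSA PD at 12 weeks or later needs no confirmation, and responses after the first progression are disregarded, so it can remove one.

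The decision boundary is narrow. At the planned 33 patients, 4 responders do not reject and 5 do, and one patient moves the ORR by 1/33, or 3.0 percentage points.

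**Working it through.** **Inputs (SAP 6, same figures in protocol 9.2).** Null ORR 5%, alternative 20%; stage 1 of 20 patients, with stopping possible at 1 or fewer responses; final rejection at 5 or more of 33. The documents give no misclassification rate, so every rate below is an assumption.

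**Step 1: reproduce the design.** For a true response probability p,

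P(reject) = Σ (x = 2 to 20) P[Bin(20, p) = x] × P[Bin(13, p) ≥ 5 − x].

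At p = 0.05:

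- x = 2: 0.1887 × 0.0245 = 0.0046
- x = 3: 0.0596 × 0.1354 = 0.0081
- x = 4: 0.0133 × 0.4867 = 0.0065
- x ≥ 5: 0.0026

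The sum is 0.0218. At p = 0.20 the same formula gives 0.802. An exhaustive minimax search with type I error at most 2.5% and power at least 80% returns this same design. The stated 2.5% is therefore the ceiling and 2.2% the attained level. No stated figure is in dispute.

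**Step 2: error rate per patient.** Let f be the assumed probability that a true non-responder ends up counted as a confirmed PSA responder. The observed response probability under the null is p = 0.05 + 0.95f.

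| f | p | Type I error |
|---|---|---|
| 0 | 0.0500 | 2.2% |
| 1% | 0.0595 | 4.2% |
| 2% | 0.0690 | 7.0% |
| 5% | 0.0975 | 20.5% |

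**Step 3: error rate per visit.** One wrong category does not make a responder, because the SAP requires confirmation. Let q be an assumed false-PR probability at each of 8 visits, independent between visits, with two in a row needed. Let a be the probability of no run of two so far with the last visit not PR, and c the same with the last visit PR. Start at a = 1, c = 0. At each visit, new a = (a + c)(1 − q) and new c = a·q. After 8 visits f = 1 − a − c, which goes into the step 2 formula.

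| q | f | p | Type I error |
|---|---|---|---|
| 1% | 0.07% | 0.0507 | 2.3% |
| 2% | 0.28% | 0.0526 | 2.6% |
| 5% | 1.67% | 0.0659 | 6.0% |

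This ignores a soft-tissue SD or PD falling between the two visits, which would block confirmation and lower f. Errors that persist within a patient, such as the same wrong reference value used at every visit, would raise f towards step 2.

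**Step 4: missed responders.** If 5%, 10% or 20% of true responders were missed (assumed), p under the alternative becomes 0.19, 0.18 or 0.16, and power falls from 80.2% to 76.2%, 71.6% or 60.8%.

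**Step 5: one patient at the boundary.** 4/33 is 12.1% (95% Clopper-Pearson interval 3.4% to 28.2%); 5/33 is 15.2% (5.1% to 31.9%). The lower limit crosses 5% between them.

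**Step 6: do existing outputs check the category?**

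- The ITT and PP sensitivity analyses of ORR (SAP 8.7.1.1) change the analysis set, not the PSA source.
- The soft-tissue response summary (Table 14.2.1.1.4) leaves PSA out, and the centrally read iRECIST ORR rests on imaging. Neither tests the PSA component.
- The by-visit split of PSA decline at 50% (SAP 8.7.3.1) uses values, but it is unconfirmed and not compared with the reported category.
- The waterfall plot is limited to measurements at or after a confirmed PSA response as defined in 8.2, so it inherits the reported category.
- Listing 16.2.6.2 shows PSA data per patient, but no rule directs anyone to reconcile it.

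**The case against.** The strongest reply is that the plan does what the protocol asks. Both objectives tables define ORR as determined by the investigator, so taking the investigator's PSA category is conformity, not departure. That stands. Making a programmed derivation the primary one after the interim analysis would be debatable, and this point does not ask for it.

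Four stronger readings are tempting, and the documents do not support them.

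- **Investigators choose their own baseline.** Protocol 9.4.1 and SAP 8.2 both fix baseline, and Appendix 9 measures the fall from it. What is missing is a check that the reported category used that baseline.
- **Independent central results are being set aside.** SAP 8.7.3.1 describes central-laboratory results entered by the investigator. The documents do not show that a complete separate central data set exists.
- **A few wrong entries take type I error to 20%.** That figure needs 5% of non-responders to be wrongly counted after confirmation. Independent visit-level errors at 5% give about 6.0%.
- **The interim decision is unsafe.** SAP 8.7.6 records that the interim was done in August 2022 and that mCRPC enrollment then stopped. Nothing in the documents shows that any patient was misclassified, and no change now alters that decision. With no formal comparison between arms, the exposure is error against the fixed 5%, not bias between arms.

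It can also be said that in arms this small a responder unsupported by PSA values would be visible in the listing. That is possible, but it relies on someone looking; the plan does not require it.

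**Conclusion.** The point holds as a weakness in the choice of analysis. A component of the primary endpoint that can be computed from recorded values is taken as reported in an open-label trial, and no planned output checks it.

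Its size cannot be fixed from the documents. For assumed rates of 1%, 2% and 5%, type I error moves from the attained 2.2% to between 2.3% and 4.2%, between 2.6% and 7.0%, and between 6.0% and 20.5%. The lower end of each range is independent visit-level error with confirmation; the upper end is that rate of patients wrongly counted after confirmation. These figures are for the planned 20 and 33. The final number of mCRPC patients and the response counts are not given, so they illustrate sensitivity and do not estimate the error in the final test.

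SAP 5 and 8.7.1.1 still plan a final mCRPC analysis with the ORR, its interval and the test, and that is the result to protect.

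**What to change.** Before the final mCRPC analysis:

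1. Reconcile the confirmation interval: at least 20 days in SAP 8.2, at least 4 weeks in Appendix 9. It matters in practice, because three-weekly visits are 21 days apart and meet the first but not the second.
2. Pre-specify an additional ORR in which PSA PR, SD and PD are derived by program from the recorded PSA values, using the SAP 8.2 baseline, the Appendix 9 percentage thresholds and the reconciled interval. Use central-laboratory values where available and flag any others.
3. Report it beside the investigator-determined ORR, which keeps its place as primary, with the same Clopper-Pearson interval.
4. List every patient whose derived and reported categories disagree, and resolve the discrepancies by query before database lock.

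The cost is some programming, a merge with central-laboratory data where these can be had, and a fallback flag for the rest. It needs no new patient data and leaves sample size, boundaries and the primary endpoint definition unchanged.
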